4.10.2. Secondary Efficacy Analyses

The TFT secondary efficacy endpoints are:

- CFB in 10MWT Speed at Week 52
- CFB in Stand from Supine Speed at Week 52
- CFB in 4-stair Climb Speed at Week 52

Descriptive statistics will be calculated for the speed and time to complete the TFT secondary efficacy endpoints as well as all CFB values by treatment group and time point.

The secondary efficacy endpoint analyses for these endpoints will be an MMRM ANCOVA, using the methodology described for the primary efficacy endpoint analysis ([Section 4.10.1](#)). The difference being that, instead of baseline NSAA as a covariate, the corresponding baseline secondary efficacy endpoint value will be used.

As described in [Section 2.6.2](#), if there are any patients not able to complete the test (reason not done = “subject physically unable to complete test”), a value of 0 will be assigned for the reciprocal test (i.e., speed in units of task per second).

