### **9.10.1. Primary Efficacy Endpoint**

The primary efficacy endpoint will be the CFB in the NSAA Total Score at Week 52.

The CFB in NSAA Total Score will be analyzed using a mixed-model repeated-measures (MMRM) analysis of covariance (ANCOVA), implemented using SAS® Proc Mixed. The factors in the model will be Baseline age ( $\leq 6.0$  years or  $> 6.0$  years), time to stand from supine ( $\leq 5$  seconds or  $> 5$  seconds), region (North America or Europe/Asia/Australia), visit, treatment group, Baseline value, Baseline value by visit, and treatment group by visit.

The primary analysis will test the treatment difference at Week 52 via the MMRM model at the two-sided 0.05 level. Details of the MMRM model will be provided in the SAP. The primary analysis will be performed on the Full Analysis Population with exclusions that may be defined in the SAP, such as excluding patients receiving treatment with eteplirsen.

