2.6.2. Secondary Efficacy Endpoints

The 3 secondary efficacy endpoints are:

- The CFB in the 10MWT speed at Week 52
- The CFB in the stand from supine speed at Week 52
- The CFB in the 4-stair climb speed at Week 52

The 10MWT measures time to walk a distance of 10 meters. The stand from supine and 4-stair climb tests measure the amount of time taken to complete those tasks. To optimize standardization and consistency of testing, study procedures must be performed by trained evaluators only, with every effort made to have the same clinical evaluator perform all assessments for a given patient, in the same order, at the same time of day, preferably in the morning. Completion of timed function tests (TFTs) is expected to take approximately 10 minutes.

For all TFTs, both the times to complete (seconds) and the speed of completing the tests (i.e., calculated as the reciprocals of the time to complete; $\text{speed} = 1/\text{time}$) will be provided. If there are any patients not able to complete the test (reason not done = “subject physically unable to complete test”), a value of 0 will be assigned for the reciprocal test (i.e., speed; in units of task per second). For the “time to complete” endpoints, a value of 12 seconds will be imputed.

Additionally, for the 3 TFTs, the time will be set to 12 seconds and the speed to 0 if the TFT assessment meets the following TFT grading criteria (i.e., each of the TFTs is “graded”):

- 10MWT: a Grade of 1 or 2 (from a 6-point scale)
 - 1=Unable to walk independently
 - 2=Unable to walk independently but can walk with knee-ankle foot orthoses or support from a person
- Stand from Supine: a Grade of 1 or 2 (from a 6-point scale)
 - 1 = Unable to stand from supine, even with use of a chair
 - 2 = Assisted Gowers – requires furniture for assist in arising from supine to full upright posture (no time to be recorded)
- 4-Stair Climb: a Grade of 1 (from a 6-point scale)
 - 1 = Unable to climb 4 standard stairs (no time recorded)

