4.2.5. Multiplicity

The following multiplicity adjustment approach will be used to strongly control the overall Type I error rate at 0.05 (two-sided) for the primary endpoint and three secondary endpoints.

A hierarchical testing procedure will be used for the secondary endpoints. At each step the test for treatment effect will be considered statistically significant if the p-value is less than or equal

to 0.05 and all previous tests also meet this level of significance. The testing hierarchy is as follows:

1. Primary endpoint: CFB in the NSAA Total Score at Week 52
2. Secondary endpoint: CFB in the Stand from Supine Speed at Week 52
3. Secondary endpoint: CFB in the 10MWT Speed at Week 52
4. Secondary endpoint: CFB in the 4-Stair Climb Speed at Week 52

This method provides strong control of the family-wise error rate at the 2-sided 0.05 level.

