4.2.11. Baseline

A patient’s baseline value will be most recent non-missing value occurring prior to initiation of study drug. In most cases this will be the value assessed at the Baseline visit. If the Baseline value is missing, the next most recent non-missing value will be used (i.e., in most cases this will be the Screening visit value).

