4.10.1. Primary Efficacy Analysis

The primary efficacy endpoint is the CFB in the NSAA Total Score at Week 52. NSAA Total Scores and the CFB values will be summarized by treatment group and time point using descriptive statistics.

If a patient initiates corticosteroid therapy or discontinues study treatment, all observations from that patient after these events will be censored from the primary efficacy analyses.

The primary efficacy endpoint analysis will be an MMRM ANCOVA. The MMRM model will include:

- CFB in the NSAA Total Score as the dependent variable
- Variables in the Model

Visit (a categorical variable)	
Treatment (edasalonexent or placebo)	Treatment \times Visit
Region (North America vs. Europe/Asia/Australia)	Region \times Visit
Baseline age (as a continuous variable),	Baseline Age \times Visit
Baseline time to stand from supine (as a continuous variable)	Baseline time to Stand \times Visit
Baseline NSAA score (as a continuous variable)	Baseline NSAA score \times Visit

- Patient as a random effect.

The primary efficacy analysis will test the difference between the edasalonexent versus placebo at Week 52 using this MMRM model.

Sample SAS code for the primary efficacy analysis is provided in [APPENDIX 1: Sample MMRM Code](#).

Descriptive summary statistics including number of patients, mean, standard error, least-square means (LS means), LS means differences, along with the p-values and corresponding 95% CIs

will be provided. Specifically, the primary efficacy endpoint hypothesis test of no treatment difference between edasalonexent and placebo is based on the least-squares means (LS-means) difference and corresponding p-value from the Week 52 visit. The results for the treatment difference for the other visits will also be provided to assess the consistency of treatment effect over different visits.

The repeated-measures analysis will be based on the restricted maximum likelihood method assuming an unstructured covariance structure to model the within-patient errors. A Kenward-Roger approximation will be used for the denominator degrees of freedom. If there is a convergence problem due to the unstructured covariance matrix, a compound symmetry covariance structure will be used to model the within-patient variance; if the compound symmetric covariance structure fails to converge, a variance components approach will be applied.

The primary efficacy endpoint analysis is an observed case analysis, with no imputation of missing data.

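### Keeping baseline NSAA in the three timed-test models is a cheap efficiency gain of unknown size; for stand-from-supine speed, the present model uses one baseline test twice and no other motor measure

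*SAP*

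**What the plan says.** SAP 4.10.2 fits an MMRM to change in each timed-test speed "using the methodology described for the primary efficacy endpoint analysis", with one substitution: "instead of baseline NSAA as a covariate, the corresponding baseline secondary efficacy endpoint value will be used". The primary model in SAP 4.10.1 contains treatment, region, age, "Baseline time to stand from supine (as a continuous variable") and "Baseline NSAA score (as a continuous variable"), each with a visit interaction. Section 4.10.2 removes the NSAA term and leaves the time-to-stand term in place.

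SAP 2.6.2 reports speeds "calculated as the reciprocals of the time to complete". SAP 4.2.11 has one rule for every baseline, the "most recent non-missing value occurring prior to initiation of study drug". In SAP 4.2.5 the step directly after the NSAA reads "Secondary endpoint: CFB in the Stand from Supine Speed at Week 52".

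Protocol 9.10.1 ends its list of model terms with "visit, treatment group, Baseline value, Baseline value by visit, and treatment group by visit", and Protocol 9.10.2 carries that model over to the secondary endpoints. SAP 4.2.4 says that models adjust for the stratification variables; time to stand is one of them (SAP 2.2).

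**The concern.** In the stand-from-supine model, baseline time T and baseline speed 1/T come from the same performance of the same test. With NSAA removed, the only other baseline covariates are region and age. The 10MWT and 4-stair climb models are better placed, because each keeps time to stand and gains its own baseline, but they lose the NSAA total too.

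The three timed tests are tested under type I error control in a fixed sequence. If stand from supine misses 0.05, neither of the other two can be claimed. A baseline covariate that explains outcome variance narrows the confidence interval without adding patients, and baseline NSAA is already in the database. What is at stake is therefore some precision on confirmatory secondary endpoints. The validity of the tests is not in question.

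**Working it through.** **1. The plan's own power figure.** SAP 4.1 gives 126 boys, 2:1, effect size 0.625, 20% dropout, two-sided 0.05 and about 80% power. Evaluable: 126 × 0.8 = 100.8, that is 67.2 and 33.6. Noncentrality: 0.625 / √(1/67.2 + 1/33.6) = 2.958. Power: Φ(2.958 − 1.960) = 84.1% (82.9% to 83.6% by noncentral t with 67:33 or 67:34). The stated figure is thus slightly conservative. It concerns the NSAA only; no SD, effect or power is given for a timed test.

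**2. Overlap of T and 1/T.** The documents give no distribution of baseline time, only an eligibility limit of 10 s. Assumed distributions:

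| Assumed baseline time | r(T, 1/T) | r² | VIF |
|---|---|---|---|
| Uniform 2–10 s | −0.919 | 0.844 | 6.4 |
| Uniform 3–10 s | −0.953 | 0.908 | 10.9 |
| Lognormal, median 5, log-SD 0.35, cut to 2–10 | −0.924 | 0.855 | 6.9 |
| Lognormal, median 5, log-SD 0.25, cut to 2–10 | −0.945 | 0.894 | 9.4 |
| Lognormal, median 4.5, log-SD 0.30, cut to 2–10 | −0.931 | 0.866 | 7.5 |

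Between 9% and 16% of the variance of 1/T is not linear in T. The terms are nearly redundant but not exactly collinear, so the model can be fitted.

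**3. What baseline NSAA could add.** Let R²p be the share of residual variance that NSAA explains beyond the covariates already present. The standard error is multiplied by √(1 − R²p), which is worth 1/(1 − R²p) − 1 more boys. The last column assumes a standardised effect of 0.625, borrowed from the NSAA for illustration.

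| R²p (assumed) | SE factor | SE reduction | Equivalent extra boys | Power |
|---|---|---|---|---|
| 0 | 1.000 | 0% | 0% | 84.1% |
| 2% | 0.990 | 1.0% | 2% | 84.8% |
| 5% | 0.975 | 2.5% | 5% | 85.9% |
| 10% | 0.949 | 5.1% | 11% | 87.7% |

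The formula ignores the cost of estimating one more coefficient. With about 101 boys that is near 1% of variance, or 0.5% of the SE, so the gain breaks even at R²p of about 1%.

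**4. Simulation.** Single-visit ANCOVA, 67:34, 4,000 runs per scenario, lognormal time (median 5 s), NSAA correlated −0.7 with log time, age and region in every model. Residual variance net of NSAA is fixed, so a useful NSAA shows up as power lost when it is omitted. Cells give power, with the mean SE in residual-SD units in brackets.

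| R²p | T + 1/T | T + 1/T + NSAA | 1/T + NSAA |
|---|---|---|---|
| 0 | 82.3% (0.2146) | 81.8% (0.2157) | 81.9% (0.2146) |
| 4.4% | 80.5% (0.2193) | 81.8% (0.2155) | 82.1% (0.2144) |
| 11.3% | 77.6% (0.2279) | 82.3% (0.2155) | 82.4% (0.2144) |

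At R²p = 0, adding NSAA raises the SE by 0.2157/0.2146 − 1 = 0.5%, as expected. Putting NSAA in place of T has no such cost. The treatment estimate was unbiased in every model. Rejection under the null was 4.8% to 5.9% (Monte Carlo SE about 0.35 points), with no pattern by covariate set. Adding 1/T to T changed the SE by less than 1%.

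**The case against.** The strongest reply is that the SAP does what the protocol asks. A single baseline term, applied to each endpoint, naturally means that endpoint's own baseline, and adjusting a change score for its own baseline is standard. Time to stand is in every model because it is a stratification factor, and speed is the right scale for a speed endpoint. All of this stands.

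The benefit is also unproven. The 10MWT and stand from supine are performed within the NSAA (Protocol 6.3.2), so NSAA may add little beyond them, and R²p could be zero. That stands too. Nor is the change entirely free: SAP 2.6.1 sets the NSAA total to missing when any item is not scored, so a boy without a scorable total at both Screening and Baseline would drop out of the timed-test models. The fallback in SAP 4.2.11 makes this unlikely but does not exclude it.

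Three stronger readings are tempting and not supported:

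- **That the collinearity damages the test.** It lies between two baseline covariates and leaves the treatment contrast unharmed.
- **That the missing power statement shows the timed tests to be underpowered.** It shows only that their power is unknown.
- **That the same change belongs in the muscle-strength, PUL and PODCI models of SAP 4.10.3.** Those endpoints are outside the testing hierarchy, so the argument from confirmatory precision does not reach them. The PUL total is analysed only in boys scoring below 6 on the entry item, expected to be a minority, where extra parameters could make the fit worse.

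**Conclusion.** The point holds as a low-cost efficiency improvement to the three timed-test models, not as the correction of an error. It is clearest for stand-from-supine speed, where the second baseline covariate adds little to the first and no other motor measure remains. For the 10MWT and 4-stair climb the case is the same in kind, but two motor baselines are already present.

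The gain in standard error is 0% to 5.1% for an assumed R²p of 0 to 10%, less about 0.5% where NSAA is added rather than exchanged for time to stand. Nothing in the documents locates R²p in that range. The simulation is a single-visit ANCOVA, not the full MMRM. The SAP's sample MMRM code (Appendix 1) was not in the text available, so how the secondary models are coded was not checked. The sample size and the primary analysis are unaffected.

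**What to change.** Before unblinding, make these edits for the three timed tests only:

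- **SAP 4.10.2:** state that baseline NSAA and its visit interaction are kept, in addition to the endpoint's own baseline and its visit interaction.
- **Stand-from-supine speed:** baseline speed may replace continuous baseline time to stand. It is a one-to-one transform of the same measurement, so the stratifier is still adjusted for. Keeping both is also acceptable.
- **SAP 4.10.4(c), as applied by 4.10.5:** give the secondary-endpoint ANCOVAs the same baseline covariates.
- **SAP 4.10.6.1 and 4.10.6.2:** add baseline NSAA to the timed-test imputation models, so that they match the analysis models.
- **SAP Section 6:** list the departure from the protocol model, beside the covariate changes already recorded there.

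The cost is a few sentences and the matching code. Each model gains at most four fixed effects (NSAA at four post-baseline visits), or none net for stand from supine if speed replaces time. No new data are needed. The number of boys lost for want of a baseline NSAA total can be counted blinded before the change is adopted.

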4.10.3. Additional Efficacy Analyses

Additional efficacy endpoints include CFB on the following:

- Muscle strength testing: 2 endpoints: elbow flexion (i.e., average of the left and right elbows), knee extension (average of the left and right knees). If either the left or right value is missing the value will be the non-missing score.

Note: values which are indicated as not being valid as determined by a response of “No” to “Was test valid? (i.e. representative of child’s true function)” for these assessments will not be included in the analysis (but will be presented in listings).

These additional efficacy endpoints will be analyzed using an MMRM ANCOVA, in a manner similar to that described in [Section 4.10.1](#) with the corresponding baseline muscle strength endpoint replacing baseline NSAA as a covariate.

- **PUL endpoints:** This includes the PUL Total Score, and the sum of individual items 1 and 2 (note these 2 items are imputed for patients who scored a “6” on Item A as defined in [Section 2.6.3.2](#)).

The sum of individual items 1 and 2, and PUL total score endpoints will be analyzed using an MMRM ANCOVA, in a manner similar to that described in [Section 4.10.1](#) with the corresponding baseline PUL score replacing baseline NSAA as a covariate.

PODCI Transfer and Basic Mobility Scale: This additional efficacy endpoint will be analyzed using an ANCOVA. The ANCOVA model will include CFB in the PODCI Transfer and Basic Mobility Scale at Week 52 as the dependent variable, treatment and region (North America vs. Europe/Asia/Australia) as factors, and baseline age (as a continuous variable), baseline time to stand from supine (as a continuous variable), and baseline PODCI Transfer and Basic Mobility Scale score (as a continuous variable) as covariates.

As an additional analysis of the PODCI Transfer and Basic Mobility Scale endpoint, the analysis above will be repeated subset to the subgroup of patients with the same caregiver completing the form at both baseline and Week 52 (i.e., from the PODCI eCRF page “Who completed this form?” with responses of: Caregiver, Father, Mother).

Note that summary statistics will be provided for the additional PODCI scales at each scheduled timepoint.

CFB multivariate rank sum score: The analysis for this Week 52 endpoint will be an ANCOVA, The ANCOVA model will include Week 52 CFB multivariate rank sum score as the dependent variable, treatment and region (North America vs. Europe/Asia/Australia) as factors, and baseline age (as a continuous variable), baseline time to stand from supine (as a continuous variable), and the corresponding rank sum of the score at baseline will be used (as described in [Section 2.6.2](#)).

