2.6.3.1. Muscle Strength Testing

Muscle strength testing will include assessment of knee extension and elbow flexion (in kilograms), and will be performed using a hand-held dynamometer. Knee myometry will be performed while the patient is in a sitting position. Elbow myometry will be performed while the patient is positioned supine.

Muscle testing will be performed by trained evaluators; every effort will be made to have the same evaluator perform all assessments for a given patient at the same time of day. Completion of each muscle test is expected to take approximately 10-15 minutes, for a total of 20-30 minutes.

Multiple assessments are taken on the right and left knee and right and left elbow. The following is the algorithm for determining the patients elbow (knee) scores:

- For both the left and right elbow (separately) the peak score (i.e., maximum value) will be used as the value for the patient.
- The average of the maximum right elbow score and maximum left elbow score will be the elbow score for that visit.
- The same algorithm is used for the knee

As such, at each scheduled timepoint, there will be an elbow flexion and knee flexion endpoint for the muscle testing (units of kilogram (kg)).

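### Muscle strength: a one-sided visit score can be set against a two-sided or opposite-side baseline, so an unchanged boy shows a change of half, or all, of his left-right difference

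*SAP*

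**What the plan says.** SAP 2.6.3.1 builds the score in two steps. First, per side: "For both the left and right elbow (separately) the peak score (i.e., maximum value) will be used as the value for the patient". Then across sides: "The average of the maximum right elbow score and maximum left elbow score will be the elbow score for that visit". For the other joint, "The same algorithm is used for the knee".

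SAP 4.10.3 introduces the endpoints with "Additional efficacy endpoints include CFB on the following" and adds the rule for incomplete data: "If either the left or right value is missing the value will be the non-missing score". Tests that the evaluator marks as not valid "will not be included in the analysis (but will be presented in listings"), so they are one possible source of a missing side.

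SAP 4.2.11 defines baseline: a patient's "baseline value will be most recent non-missing value occurring prior to initiation of study drug". The model is the repeated-measures model of SAP 4.10.1, with the baseline strength score in place of baseline NSAA as covariate. None of these sections requires the same side or sides at baseline and at the visit.

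**The concern.** Change from baseline means something only if the same quantity is measured twice. Here the quantity can switch from a two-limb mean to one limb, or from one limb to the other, and the boy's left-right difference then enters his recorded change. The covariate does not remove this, because it is the overall baseline score and carries no side information. No planned analysis would expose it: the sensitivity analyses in SAP 4.10.4 and 4.10.5 and the COVID-19 analyses in SAP 5.3 cover only the primary and secondary endpoints.

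Baseline itself can be affected. Protocol Appendix 1 schedules strength testing at both Screening and Baseline. If SAP 4.2.11 is applied to the joint score, a one-sided Baseline score counts as non-missing, and a complete two-sided Screening test is passed over.

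Elsewhere the SAP is stricter. An NSAA total with an unscored item is set to missing (2.6.1), and PODCI has an extra analysis restricted to the same caregiver at both times (4.10.3). What is at stake is the accuracy of individual changes, and some precision, in two additional endpoints.

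**Working it through.** The plan gives no strength figure to reproduce, so the check is algebra on the scoring rule, followed by a sizing under stated assumptions.

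**1. False change in one boy.** Let true strengths L and R stay constant.

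- Two-sided baseline, right only at the visit: R − (L+R)/2 = (R−L)/2.
- Two-sided baseline, left only at the visit: (L−R)/2.
- Right only at baseline, both at the visit: (L+R)/2 − R = (L−R)/2.
- Right only at baseline, left only at the visit: L − R, the full difference.
- Same single side at both times: 0.

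| L, R (kg) | Two-sided baseline | Right only at visit | Left only at visit | Baseline right, visit left |
|---|---|---|---|---|
| 4, 4 | 4.0 | 0 | 0 | 0 |
| 4, 5 | 4.5 | +0.5 | −0.5 | −1 |
| 4, 6 | 5.0 | +1.0 | −1.0 | −2 |

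For the 4/6 kg boy, +1 kg is 1/5 = 20% of baseline. Side-matched change is 6 − 6 = 0.

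**2. Effect on an arm mean.** Let p be the share of boys with a two-sided baseline and one side missing at the visit (assumed; not in the documents). If the missing side is random, the mean error is 0 and the added variance is p × (|R−L|/2)²; for p = 5% and 1 kg, 0.05 × 0.5² = 0.0125 kg². If the weaker side were always the missing one, the arm mean would shift by p × |R−L|/2:

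- p = 5%, 1 kg: 0.05 × 0.5 = 0.025 kg.
- p = 10%, 2 kg: 0.10 × 1 = 0.10 kg.

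Equal shifts cancel between arms. With 10% in one arm and 5% in the other, at 2 kg, the contrast would move by (0.10 − 0.05) × 1 = 0.05 kg.

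**3. Effect on variance.** Assumptions: mean 5 kg; SD of the left-right difference d = 0.5 or 1.0 kg (10% or 20% of the mean); SD of true change 0.8 kg (variance 0.64); per-side measurement noise SD s; baseline two-sided; a random side missing in a share p of 5% to 20%. These are variances of raw change at one visit, before covariate adjustment.

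With noise on every measurement at both times:

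- both sides at the visit: 0.64 + s²
- one side, SAP rule: 0.64 + d²/4 + 1.5s²
- one side, side-matched: 0.64 + 2s²

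Results at p = 20%:

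- s = 0.3, d = 1.0: SAP 0.8 × 0.73 + 0.2 × 1.025 = 0.789; matched 0.8 × 0.73 + 0.2 × 0.82 = 0.748; ratio 1.055.
- s = 0.3, d = 0.5: 0.7515/0.748 = 1.005.
- s = 0.5, d = 0.5: 0.9275/0.940 = 0.987, so the SAP rule has the lower variance.

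If baseline is treated as error-free and s = 0.3 enters only at the visit, the terms become 0.64 + s²/2, 0.64 + d²/4 + s² and 0.64 + s². At d = 1.0 and p = 20%: (0.8 × 0.685 + 0.2 × 0.98)/(0.8 × 0.685 + 0.2 × 0.73) = 0.744/0.694 = 1.072. At d = 0.5 and p = 5% the ratio is 1.005.

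Break-even with noise at both times: d²/4 = s²/2, so s = d/√2, about 0.7d. Above that noise level, side-matching is slightly less precise than the SAP rule.

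**The case against.** The rule is pre-specified, keeps data and applies identically to both blinded arms. Several attempts are made per side and the peak is taken (SAP 2.6.3.1), so one failed attempt need not lose a side. The SAP does not say that validity is recorded by side; if it is recorded for the whole test, both sides drop and no mismatch arises from that source. The COVID-19 priority lists in Protocol Appendix 2 name the NSAA, the timed tests and the PUL but not muscle strength, so pandemic losses would probably remove the whole test. Muscle strength is outside the testing hierarchy of SAP 4.2.5 and is not a component of the rank-sum endpoint (2.6.3.4). Even the largest variance ratio, 1.072, is only about 3.5% in standard error (√1.072 = 1.035), and side-matching can cost precision.

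All of that stands on frequency and consequence. It does not touch the algebra: the SAP wrote a rule for one-sided values, and that rule returns a change that did not happen whenever the sides differ in strength and are not matched.

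A reader might infer that the rule flatters boys with a failing limb, because the weaker side would be the one lost. The documents do not support this. The validity question asks whether a test reflected what the child can really do, and a truly weak limb can give a valid low value, which is kept. Nothing shows that the weaker side is lost more often.

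**Conclusion.** The scoring defect is certain, and its consequence is limited. An unchanged boy is recorded as changing by half his left-right difference, or by all of it with opposite single sides, and nothing else in the SAP corrects this. The effect is confined to elbow flexion and knee extension; the primary and secondary conclusions are not affected.

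A reader might also infer a biased treatment effect. That would require the frequency of one-sided values, or the side lost, to differ by arm, and nothing in the documents indicates either. Otherwise the rule adds error to individual changes.

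The trial-level size is unknown, because asymmetry, noise and frequency are not given. Across the assumptions tested, the variance of change runs from about 1% lower to 7% higher than with side-matching. The reason to amend is that like-for-like change removes the artefact whichever side is missing, at low cost, and not that precision would improve markedly.

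**What to change.** In SAP 2.6.3.1 and 4.10.3, replace the single-side substitution with side-matched change:

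- For each joint and visit, compute change from baseline separately for left and right, using only sides valid at both baseline and that visit, and average the available side changes.
- Take each side's baseline as its last valid pre-dose value, using Screening where the Baseline value for that side is missing.
- Keep one fixed baseline strength score per boy as the model covariate. A covariate that changed with the sides available at each visit would complicate the baseline-by-visit term for little gain.
- Report the number of one-sided scores by arm and visit, and state whether validity is recorded by side.

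The cost is a few sentences and minor programming. No new data are needed, because the SAP already takes separate left and right peaks. Boys with both sides valid throughout are unaffected. There are two downsides. A boy with no side valid at both times has no change value at that visit. A one-sided baseline is also slightly noisier than a two-sided one, so precision could fall slightly if per-side noise SD exceeds about 0.7 times the SD of the left-right difference. Setting the score to missing whenever a side is absent would also remove the false change, but it discards the valid side.
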